4.2.3 Secondary analysis

The secondary endpoints include:

- a. The proportion of children experiencing a recurrent urinary tract infection at any time after the TOC visit.
- b. The proportion of children with asymptomatic bacteriuria at the TOC visit.
- c. The proportion of children that develop the gastrointestinal colonization of antimicrobial resistant *Escherichia coli* (*E. Coli*) and *Klebsiella pneumoniae* (*K. Pneumoniae*) assessed through Outcome Assessment visit (Day 24-30).
- d. The proportion of children presenting with clinical symptoms that may be related to UTI prior to or at the TOC visit.
- e. The proportion of children with positive urine culture prior to or at TOC visit.

The secondary analysis for recurrent infection (Table 5 in Section 7.1), asymptomatic bacteriuria (Table 6 in Section 7.1), presenting with clinical symptoms (Table 7 in Section 7.1), and positive urine culture (Table 8 in Section 7.1) (Endpoints a, b, d and e), will include conventional tests to evaluate whether the proportions between two treatment arms are equal. These tests will be conducted by calculating the two-sided 95% confidence limit for the difference between the short-course and standard-of-care therapies. Analyses will be performed on per-protocol population, with appropriate exclusions of treatment failures. Details of these exclusions are shown in Section 5.1.

The secondary analysis for proportion of children that become colonized with antibiotic-resistant *E. coli* and *Klebsiella pneumoniae* assessed through Outcome Assessment visit (Day 24-30) (Endpoint c) will consist of two-sample tests for differences between proportions, using a chi-square test at significance level of 0.05 (Table 9 in Section 7.1). We hypothesize that children with short-course therapy will be less likely to become colonized with emergent antibiotic-resistant *E. coli* and *K.*

pneumoniae. These analyses will examine whether antibiotic resistance after enrollment emerges differently between the short course and standard of care arms. First, a summary of antibiotic resistance present at enrollment, TOC and Outcome Assessment among the per-protocol population excluding treatment failures with a sample at TOC (Population 4) will be presented (*Table 9 in Section 7.1*).

Emergent antibiotic resistance will be defined as follows:

Among Population 4 (per-protocol population excluding treatment failures without TOC sample), define an indicator for emergent antibiotic resistance at TOC and Outcome Assessment. A child would have emergent antibiotic resistance if they

1. Had no antibiotic-resistant E.coli or K.pneumoniae at enrollment but one or both are now present. OR
2. Had either antibiotic-resistant E.coli or K.pneumoniae at enrollment but now the other antibiotic-resistant organism is present OR
3. Had antibiotic-resistant E.coli and/or K.pneumoniae at enrollment, but have now developed resistance to new antibiotics in either organism.

Emergent antibiotic resistance will be examined by treatment arm in Table 10. We also want to show which antibiotics the organism showed resistance (ceftazidime, amoxicillin-clavulanate, TMP-SMX, or ampicillin). Prior to unblinding, patterns of multiple resistance will be summarized and if there are a few very common patterns they will also be included in this table (*Table 11 in Section 7.1*).

Longitudinal models such as mixed-effects logistic regression models and logistic regression models with generalized estimating equation (GEE) will be explored to analyze the repeated outcome of emergent antibiotic resistance.

In some cases, subjects who experienced treatment failure will not be evaluable for the secondary objectives. Specifically:

- Recurrent infection: Subjects with treatment failures will not be evaluable for recurrent infection.
- Asymptomatic bacteriuria: subjects with treatment failure will be evaluable (all will be negative for asymptomatic bacteriuria – by definition, treatment failures are symptomatic so cannot be considered to have asymptomatic bacteriuria).
- Colonization: Generally, subjects with treatment failure will not be evaluable for colonization. However, one exception would be that if the child completes the Test of Cure visit but is a treatment failure, we collect a stool specimen at that visit and thus will have a specimen to evaluate for colonization with resistant bacteria.
- Clinical symptoms: subjects with treatment failure will be evaluable (all will be positive for clinical symptoms).
- Positive Cultures: subjects with treatment failure will be evaluable (all will have positive cultures).

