4.2.5 Sub-population analyses

Treatment effects for the primary and secondary endpoints will be estimated as differences between proportions and compared for subpopulations defined by age (defined initially as less than 3 years old, 3 to 6 years old, and 7 to 10 years old), febrile or non-febrile UTI, type of originally prescribed antibiotic, and site. First, proportions will be tabulated as two-sample comparisons and chi-square tests for treatment differences in the endpoints within subgroups will be calculated (*Table 12-*

17 in Section 7.1). Factors where significant differences are observed will be further assessed using logistic regression analysis (*Table 18-23 in Section 7.1*). Goodness of fit test will be reported for model checking. Treatment-by-subpopulation interactions will be tested using likelihood ratio tests. The power of these comparisons is expected to be low for both primary and secondary endpoints. The study is only likely to detect marked differences in treatment effects in these subpopulations. These analyses will use only the per-protocol population with appropriate exclusions (see Section 5.1). Because these analyses are exploratory, significance level at 0.05 will be used.

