5.1 Tables

▪ Definition of populations

- **Population 1:** All subjects taking at least one dose of study treatment between Day 6 and Day 10 who have been evaluated for treatment success at TOC or have failed prior to TOC (ITT population)
- **Population 2:** The enrolled subjects who were adherent to their assigned study regimen and completed more than 80% of the prescribed dose between Day 6 and Day 10 (per-protocol population)
- **Population 3:** Subjects in population 2 who did not experience a treatment failure.
- **Population 4:** Subjects in population 2 who have a stool sample at TOC visit. Some treatment failures will not have a sample collected at TOC because they failed prior to TOC. Treatment failures without the sample at TOC would be excluded from population 4.

▪ Definition for a subject having primary endpoint

The primary endpoint of this study is the proportion of children experiencing treatment failure (symptomatic UTI) at the TOC visit (Day 11-14).

▪ Data handling

- Treat blanks and “.” as missing unless specified otherwise.

6. References

1. [name] R, Chan E. A meta-analysis of randomized, controlled trials comparing short- and long-course antibiotic therapy for urinary tract infections in children. *Pediatrics*. May 2002; 109(5):E70-70.

7. Appendices

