Antibiotic Type TMP-SMX Amoxicillin-Clavulanate Cefixime Cefdinir Cephalexin			
Site CHOP PITT			

Table 15. Comparison of the proportion of subjects with clinical symptoms that may be related to a UTI prior to or at the TOC visit for subpopulation (Population 2) (Secondary endpoint d)

	Arm 1: Standard Course Total= xxx N (%)	Arm 2: Short Course Total= xxx N (%)	p-value for Chi-square test
Age Group 2 month – 35 months 3 – 6 years 7-10 years			
Febrile Febrile UTI Non-Febrile UTI			
Antibiotic Type TMP-SMX Amoxicillin-Clavulanate Cefixime Cefdinir Cephalexin			
Site CHOP PITT			

Table 16. Comparison of the proportion of subjects with positive urine cultures prior to or at the TOC visit for subpopulation (Population 2) (Secondary endpoint e)

	Arm 1: Standard Course Total= xxx N (%)	Arm 2: Short Course Total= xxx N (%)	p-value for Chi-square test
Age Group 2 month – 35 months 3 – 6 years 7-10 years			
Febrile Febrile UTI Non-Febrile UTI			
Antibiotic Type TMP-SMX Amoxicillin-Clavulanate Cefixime Cefdinir Cephalexin			
Site CHOP PITT			

Table 17. Comparison of Risk of emergent colonization with antimicrobial resistant E. coli or K. pneumoniae in Gastrointestinal Tract for Subpopulations (Population 4) (Secondary endpoint c)

	Arm 1: Standard Course Total= xxx N (%)		Arm 2: Short Course Total= xxx N (%)		p- value 1	p- value 2
	TOC visit	Outcome visit	TOC visit	Outcome visit		
Age Group						
2 – 35 months						
3 – 6 years						
7-10 years						
Febrile						
Febrile UTI						
Non-Febrile UTI						
Antibiotic Type						
TMP-SMX						
Amoxicillin- Clavulanate						
Cefixime						
Cefdinir						
Cephalexin						
Site						
CHOP						
PITT						

p-value 1 and p-value 2 will reported from Chi-square test comparing the proportions between sub-populations and treatment arms at TOC visit, and Outcome assessment visit, respectively.

Table 18. Multivariable Logistic Regression Analysis for Treatment failure (Symptomatic UTI at TOC visit) (Population 1) (Primary endpoint)

	Odds ratio	95% CI	p -value
Arm 1 Standard Course(reference)			
Arm 2 Short Course			
Covariates			

Interaction Term			

CI: Confidence Interval

SAS tips: SCALE=NONE in the MODEL statement of the PROC LOGISTIC procedure to generate deviance and Pearson chi-square for goodness of fit test.

Table 19. Multivariable Logistic Regression Analysis for Recurrent Infection at any time after the TOC visit (Population 3) (Secondary endpoint a)

	Odds ratio	95% CI	p -value

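### No secondary efficacy endpoint has a planned between-arm comparison in Population 1, and the adherence-selected sets used instead can drop children because they failed treatment

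*SAP*

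**What the plan says.** **Populations (SAP 5.1).** Population 1 is dosed children "who have been evaluated for treatment success at TOC or have failed prior to TOC (ITT population". Population 2 is children who were adherent and "completed more than 80% of the prescribed dose between Day 6 and Day 10 (per-protocol population". Population 3 is "Subjects in population 2 who did not experience a treatment failure". Population 4 is the part of Population 2 with a TOC stool, and the SAP adds: "Treatment failures without the sample at TOC would be excluded from population 4".

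**Secondary analyses (SAP 4.2.3).** For endpoints a, b, d and e: "Analyses will be performed on per-protocol population, with appropriate exclusions of treatment failures". Endpoint c, resistant colonisation, rests on Population 4. For subgroups, SAP 4.2.5 says: "These analyses will use only the per-protocol population with appropriate exclusions (see Section 5.1".

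**Failures (SAP 4.2.3).** They are not evaluable for recurrence. For endpoint e the text reads: "Positive Cultures: subjects with treatment failure will be evaluable (all will have positive cultures". Endpoint d (symptoms) has a parallel rule.

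**Protocol.** Sections 6.4.4 and 8.2 stop study product when a symptomatic UTI is confirmed on Days 6-10. Section 12.4 sets no adherence limit on the secondary tests, and it keeps children who stop treatment in follow-up with endpoints assessed. It also treats finding no difference in symptoms and cultures as showing that short course is not inferior. Failures still give a stool at Day 24-30 (Protocol Summary and section 8.4).

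**The concern.** Populations 2, 3 and 4 are all selected after randomisation on how much study product was taken. For symptoms and cultures, the SAP's evaluability rule and its analysis set conflict: failures are to count as positive, but a failure stopped early may not be in the set. The outcome can then cause the exclusion, in a comparison whose null result the protocol would read in favour of short course.

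Recurrence has a second, separate problem. TOC on Day 11-14 falls 6-9 days after the last active dose in the short arm (Day 5) but 1-4 days after it in the standard arm (Day 10). The same late relapse can be a failure, and so excluded, in one arm, and a counted recurrence in the other. No table adds the two periods. A Population 2 total can be built from shell Tables 4 and 5, but a Population 1 total cannot.

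**Working it through.** **1. The plan's own figure.** With failure 5% in both arms, margin 5 points, one-sided alpha 0.05 and 90% power (SAP 3.2): n = (1.645 + 1.282)² × 2 × 0.05 × 0.95 / 0.05² = 325.4, so 326 per arm, as stated. The plan gives no such figure for any secondary endpoint. I use 326 per arm below.

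**2. Population named in each shell (SAP 7.1).**

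| Endpoint | Main | Subgroup | Model |
|---|---|---|---|
| a, recurrence | Table 5: Pop 3 | 13: Pop 3 | 19: Pop 3 |
| b, asymptomatic bacteriuria | 6: Pop 2 | 14: Pop 2 | 20: Pop 2 |
| d, symptoms | 7: Pop 2 | 15: Pop 2 | 21: Pop 2 |
| e, cultures | 8: Pop 2 | 16: Pop 2 | 22: Pop 2 |
| c, resistance | 9: Pop 2 in title, Pop 4 in SAP 4.2.3; 10-11: Pop 4 | 17: Pop 4 | 23: Pop 4 |

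Among efficacy tables, Population 1 appears only for the primary endpoint: Table 3, and Table 18, headed "Treatment failure (Symptomatic UTI at TOC visit) (Population 1) (Primary endpoint". Table 18 itself conflicts with the per-protocol-only rule in SAP 4.2.5.

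**3. Dose arithmetic.** Completing Days 6-8 gives 3/5 cefixime, 6/10 TMP-SMX or 9/15 cephalexin doses. Each is 60%, below either cut-off. Completing Day 9 gives 4/5, 8/10 or 12/15, exactly 80%. That passes the protocol's rule of at least 80% and matches the dose counts in the SAP 4.2.2 adherence table, but it fails the SAP's wording of more than 80%.

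**4. Effect on Table 8.** Let f be the failure rate (5% standard; 7% or 9% short, inside the plan's 5-9%) and g the share of failures leaving Population 2. Assume other positive cultures in 5% of children in each arm. Then

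Population 2 rate = (f(1 − g) + 0.05) / (1 − gf).

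The last column is the chance that a two-sided 95% Wald interval shows a short-arm excess (exact binomial enumeration, n reduced for exclusions).

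| f short / standard | g short / standard | Rates | Difference (points) | Chance |
|---|---|---|---|---|
| 9% / 5% | 0 / 0 (Population 1) | 14.0% vs 10.0% | 4.0 | 35% |
| 9% / 5% | 10% / 10% | 13.2% vs 9.5% | 3.7 | 31% |
| 9% / 5% | 25% / 25% | 12.0% vs 8.9% | 3.2 | 26% |
| 9% / 5% | 40% / 40% | 10.8% vs 8.2% | 2.6 | 20% |
| 9% / 5% | 40% / 10% | 10.8% vs 9.5% | 1.2 | 7% |
| 9% / 5% | 10% / 40% | 13.2% vs 8.2% | 5.1 | 55% |
| 7% / 5% | 0 / 0 (Population 1) | 12.0% vs 10.0% | 2.0 | 13% |
| 7% / 5% | 25% / 25% | 10.4% vs 8.9% | 1.6 | 10% |

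**5. When does the difference shrink?** Near g = 0 the rate falls by about g × f × (1 − f − 0.05). The difference is therefore unchanged when g standard / g short = f_short(0.95 − f_short) / (0.05 × 0.90):
- 9%: 0.0774 / 0.045 = 1.72
- 8%: 0.0696 / 0.045 = 1.55
- 7%: 0.0616 / 0.045 = 1.37
- 6%: 0.0534 / 0.045 = 1.19

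Below that ratio the difference shrinks, and above it the difference grows.

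**6. How large could g be?** The documents do not say. Assume onset is uniform from the first Day 6 dose to TOC (120 h for Day 11, 192 h for Day 14), the child is seen 0-36 h later (Protocol 8.2), and the culture is read at 18-24 h (Protocol 9.2.1). The mean delay to stopping is 18 + 21 = 39 h. With evenly spaced doses, share lost = (time of qualifying dose − 39) / window.
- More than 80%: qualifying dose at 96 h for every drug; 57/192 to 57/120 = 30-48%.
- At least 80%: cefixime 72 h, 33/192 to 33/120 = 17-28%; TMP-SMX 84 h, 45/192 to 45/120 = 23-38%; cephalexin 88 h, 49/192 to 49/120 = 26-41%.

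**7. Recurrence timing.** Assume equal UTI totals of 13%, split as failures plus recurrences 8 + 5 (short) and 5 + 8 (standard).
- Failures excluded: 0.05/0.92 = 5.4% vs 0.08/0.95 = 8.4% (n 300 vs 310). The interval favours short course 30% of the time.
- All children kept: 5% vs 8%, 35%.
- Cumulative endpoint: 13% vs 13%, 2.5%.

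For totals of 12% (7 + 5 vs 5 + 7) the figures are 17%, 19% and 2.5%.

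**The case against.** - **Outcomes by arm are promised elsewhere.** SAP 4.2.1 and Protocol 12.4 plan descriptive outcome statistics within each treatment group without an adherence limit. True, but they name no population for these, and no shell covers secondary outcomes. The ITT imputation text in SAP 4.2.6 concerns the primary endpoint.
- **Failures are not hidden.** Table 3 shows every failure to TOC in Population 1 by arm, and Table 4 repeats this in Population 2. This stands: a reader might infer that the primary conclusion is compromised, and it is not.
- **Direction is unknown.** A reader might infer that the per-protocol tables must favour short course. The documents do not support that. One arm takes placebo and the other active drug on Days 6-10, so onset and stopping may differ. If short-arm relapse began 48 h after the first Day 6 dose while standard-arm onset stayed uniform, then under the more-than-80% rule the short arm would lose about 7-14% of failures and the standard arm 30-48%. The difference would then be inflated to about 5 points.
- **The share lost may be small.** The 30-48% range uses the stricter cut-off, although the SAP's own dose counts are exactly 80%. An extra 24 h before stopping would cut the loss under the at-least-80% rule to between 9/192 = 5% and 25/120 = 21%. It falls towards 0 if failures are first found at TOC.
- **Some exclusions are defensible.** Failures are treated outside the protocol, so excluding them from recurrence, or their later stools from the main resistance table, is reasonable. A cumulative UTI count is not on the protocol's endpoint list.
- **Power is low anyway.** Even in Population 1 the chance of showing 9% versus 5% in endpoint e is 35%. Reading a null result as non-inferiority is a separate weakness.

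**Conclusion.** The point holds as a gap in the planned analyses. The populations named in the shells leave no secondary endpoint with a Population 1 comparison, and for symptoms and cultures the SAP's evaluability rule conflicts with its analysis set.

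The size and direction of any bias in Tables 7 and 8 are not established. Under the stated assumptions a 4.0-point difference becomes 2.6 to 3.7 points with equal loss of 10-40%, and 1.2 to 5.1 points with unequal loss. The break-even ratio of about 1.7 applies only at 9% versus 5%; it is about 1.4 at 7% and 1.2 at 6%. The share lost is an assumption throughout.

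The recurrence artefact is a matter of endpoint definition. A reader might infer that moving to Population 1 cures it, but keeping all children raises the false signal from 30% to 35% in the example. Only the cumulative count brings it back to 2.5%. The equal totals in that example are constructed to isolate the timing effect.

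**What to change.** 1. Add Population 1 versions, by randomised arm, of the tables for endpoints b to e, among children with the data each needs. Report them beside the per-protocol tables, because neither set alone is conservative: standard-arm children who stop early also pull Population 1 towards no difference.
2. Add a supplementary Population 1 table of any symptomatic UTI from Day 6 to Day 38-44, counting failures as events, and interpret the Population 3 recurrence table alongside it.
3. As a sensitivity analysis, add Day 24-30 emergent resistance in all dosed children with enrolment and Day 24-30 stools, whether or not they failed or gave a TOC stool. Note that failures' stools also reflect non-study treatment.
4. Reconcile the adherence cut-off: at least 80% in Protocol 12.4 and in the SAP 4.2.2 dose counts, against more than 80% in the text of SAP 4.2.2 and 5.1. This decides whether 4/5, 8/10 or 12/15 doses is per-protocol. Also reconcile the Table 9 population (SAP 4.2.3 against the shell) and the Table 18 population (SAP 4.2.5 against the shell).

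The cost is SAP wording and a few more shells; all data are already collected. The cumulative endpoint mixes relapse with new infection, which the table should state.

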4.2.1 Primary and Secondary Outcome Measures

The primary outcome measure is:

- Comparison of efficacy based on symptomatic UTI as assessed at the TOC visit (Day 11-14), between short-course and standard-course of antibiotics.

Since the primary objective of the study is to establish that short-course therapy is as effective as the standard therapy, the analysis of the primary endpoint will be based on a non-inferiority test. The primary analysis will be done on the intent to treat (ITT) population.

The secondary outcome measures are:

- Comparison of the number of subjects that have a recurrent infection (includes a relapse UTI or a reinfection) at any time after the TOC visit (Day 11-14), following short-course versus standard-course of antibiotics.
- Comparison of the number of subjects that become colonized with antimicrobial resistant *Escherichia coli* (*E. coli*) and *Klebsiella pneumoniae* (*K. pneumoniae*) in the gastrointestinal tract as assessed through Day 24-30, following short-course versus standard course of antibiotics.
- Comparison of the number of subjects with asymptomatic bacteriuria at the TOC visit, following short-course versus standard-course of antibiotics.

-
- Comparison of the number of subjects with clinical symptoms that may be related to a UTI prior to or at the TOC visit, following short-course versus standard-course of antibiotics.
 - Comparison of the number of subjects with positive urine cultures prior to or at the TOC visit, following short-course versus standard-course of antibiotics.

For a summary of individual subject study outcomes against the primary outcome measure see Table 2.

Sub-study Outcome Measures:

Seattle Children’s Hospital R21

- Presence of *E. coli*, presence of *K. pneumoniae*
- Sub-types of *E. coli* (0=phylogroups A or B1, 1=phylogroups B2 or D), sub-types of *K. pneumoniae*
- Presence of treatment-susceptible *E. coli*, presence of treatment-susceptible *K. pneumoniae*
- Presence of treatment-resistant *E. coli*, presence of treatment-resistant *K. pneumoniae*

Carbapenem resistant Enterobacteriaceae study

- Prevalence of colonization with carbapenem resistant *Enterobacteriaceae* in children after completion of the course of antibiotic therapy for UTI

Microbiome pilot study

- Comparison of the overall biodiversity of the gut microbial community, as measured by culture-independent marker gene sequencing at each follow-up visit following short-course and standard-course antibiotic exposure.

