The secondary outcome measures of this trial are provided above. A difference between the two arms with regards to asymptomatic bacteriuria, presence of clinical symptoms, and negative urine culture is not expected. No difference will mean that shorter courses of antibiotics for treatment are not inferior to long courses in eradicating bacteria from the urinary tract as well as impacting clinical symptoms. This analysis will be a conventional test for efficacy and will consist of a straightforward two-sample test for a difference between proportions, using a two-sided chi-square test at significance level of .05.

Sub-study Analysis:

Seattle Children’s Hospital R21

As previously noted, patient stool samples will be collected on 3 occasions. For primary analysis, cross-sectional analysis will be performed, i.e. looking at samples from one occasion at a time.

For each occasion, the following proportions will be summarized:

- 1) Among all patients, proportion of patients with *E. coli* detected, proportion of patients with *K. pneumoniae* detected, and same proportions within each treatment arm.
- 2) Among patients with *E. coli* detected, proportions of sub-type 0 or sub-type 1; among patients with *K. pneumoniae* detected, proportions of the two sub-types, and same proportions within each treatment arm.
- 3) Among patients with *E. coli* detected, proportions of treatment-susceptible *E. coli*; among patients with *K. pneumoniae* detected, proportion of treatment-susceptible *K. pneumoniae*; and same proportions for different treatment arms.
- 4) Among patients with *E. coli* detected AND treatment-susceptible, proportions of sub-type 1; among patients with *K. pneumoniae* detected AND treatment-susceptible, proportions of sub-type 1; and same proportions for different treatment arms
- 5) Among patients with *E. coli* detected proportion of treatment-resistant *E. coli*; among patients with *K. pneumoniae* detected, proportion of treatment-resistant *K. pneumoniae*; and same proportions within different treatment arms.

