16 DATA HANDLING AND RECORD KEEPING

16.1 Data Management Responsibilities

The CHOP Biostatistics and Data Management Core (BDMC) facility will provide analytical, data management and information technology support.

The objectivity and independence in carrying out statistical support and data management services is ensured through the creation and implementation of the Statistical Analysis Plan (SAP) and Data Management Plan (DMP). The SAP is a written document describing the analyses to be performed for this study. Before any analyses (including interim analyses) begin, the Protocol Biostatistician will develop the SAP in conjunction with other applicable project staff, following the BDMC Standard Operating Procedure (SOP). The SAP addresses statistical analysis considerations such as: justification for the sample size; populations considered for the analysis of efficacy and safety; definitions of eligibility and evaluability, data handling and statistical methods, specifications for how to handle missing data, planned reasons for excluding subjects for whom data are available from analysis, summary of method of analyses, including statistical tests for each of the outcome measures outlined in the protocol, planned analyses of subgroups and project center effects; and justification for adjustment or lack of adjustment to the significance level for multiple comparisons.

The BDMC data management team, led by a Clinical Data Manager (CDM), will develop a Data Management Plan (DMP) that provides information on study objectives; the scope of work; responsibilities; applicable BDMC SOPs; scheduled study visits and required CRFs; data handling conventions; and communication and coordination plans with NIAID/DMID, Principal Investigators (PIs), sites, and internal study staff. The DMP serves as a reference guide to the operational procedures governing the life-cycle of data management activities for the study. This comprehensive plan encompasses all data management phases and facets of the study to ensure high standards of data quality. Having these data management policies and procedures documented prior to the start of data collection, updated as necessary during the study, and monitored for compliance throughout the study, ensures objectivity and independence while carrying out data management services.

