2.2.4 Secondary outcomes

The secondary outcome measures are:

- a. Recurrent infection (includes a relapse UTI or a reinfection) at any time after the TOC visit (Day 11-14)
- b. Asymptomatic bacteriuria at the TOC visit
- c. Colonization with antimicrobial resistant E.coli and K. pneumoniae in the gastrointestinal tract as assessed through Day 24-30.
- d. Presentation of clinical symptoms that may be related to UTI prior to or at the TOC visit
- e. Positive urine culture prior to or at the TOC visit

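### Resistance endpoint c is defined per child through Day 24-30, but every planned output is by visit and none is named as its test

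*SAP*

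**What the plan says.** **Definition.** Protocol 4.2.1 counts subjects who become colonized with resistant *E. coli* and *K. pneumoniae* "in the gastrointestinal tract as assessed through Day 24-30, following short-course versus standard course of antibiotics". SAP 2.2.4 uses the same time frame ("in the gastrointestinal tract as assessed through Day 24-30"), and SAP 4.2.3 words the endpoint as the proportion of children who develop such colonization, "assessed through Outcome Assessment visit (Day 24-30").

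**Test.** SAP 4.2.3 states: "Endpoint c) will consist of two-sample tests for differences between proportions, using a chi-square test at significance level of 0.05". It cites Table 9 for this. Protocol 12.4 makes the secondary chi-square test two-sided ("using a two-sided chi-square test at significance level of .05").

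**Hypothesis.** SAP 4.2.3 expects children on short course to be less likely to become colonized with emergent resistant organisms. It then describes Table 9 as a summary of the resistance present at the three visits.

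**Emergent resistance.** The SAP will "define an indicator for emergent antibiotic resistance at TOC and Outcome Assessment", by comparing the child's status at that visit with enrolment. The result goes to Table 10, and its breakdown by agent to Table 11. Mixed-effects and GEE logistic models for the repeated outcome are to be explored.

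**Multiplicity.** Protocol 16.1 lists among the contents of the SAP a "justification for adjustment or lack of adjustment to the significance level for multiple comparisons".

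**The concern.** A proportion that develops an event through a time point is a cumulative quantity. A child with emergent resistance at TOC who is clear at Day 24-30 has met the endpoint, and so has a child who is clear at TOC and positive at Day 24-30. A by-visit table counts each of these children in one row only, so neither row gives the defined proportion.

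The test is also not tied to one comparison. The table cited for the 0.05 test shows prevalence, including resistance already present before study product. The table that shows emergence has two p-values. If one visit row is significant and the other is not, the plan does not say whether the hypothesis is supported.

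This matters because resistance is the programme's reason for studying shorter courses: it is in the protocol title and in the rationale (Protocol 2.2). A reader will look to this endpoint for the benefit of short course.

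**Working it through.** **1. Definition against outputs**

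| Output (SAP 7.1) | What the rows are | Combines TOC and Day 24-30? |
|---|---|---|
| Table 9 | Prevalence of resistance, 6 rows at each of 3 visits | No |
| Table 10 | Emergent resistance, one row per visit | No |
| Table 11 | Emergent resistance by agent, 4 rows per visit | No |
| Table 17 | Emergent resistance by subgroup, one column per visit in each arm | No |
| Table 23 | Logistic model, repeated separately by visit | No |

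The titles of Tables 9 to 11 say through the Outcome Assessment visit, but every row is a single visit.

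**2. Why by-visit proportions do not give the cumulative one.** If p1 and p2 are the proportions with emergent resistance at TOC and at Outcome Assessment, the proportion with either lies between max(p1, p2) and min(1, p1 + p2). For illustration, assume p1 = p2 = 10%. The cumulative proportion could then be anything from 10% to 20%, and would be 0.10 + 0.10 − 0.10 × 0.10 = 19% if the visits were independent. The documents give no resistance rates, so these inputs are assumptions. The overlap must be counted child by child.

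**3. Count of comparisons.** The documents state no number of tests, error rate or power for endpoint c, so there is no figure of theirs to reproduce. From the shells:

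- Table 9: 6 × 3 = 18. Six of these are at enrolment, before study product starts on Day 6, which leaves 12.
- Table 10: 2.
- Table 11: 4 × 2 = 8.
- Post-enrolment total: 12 + 2 + 8 = 22. Emergent resistance only (Tables 10 and 11): 2 + 8 = 10.

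Table 17, Table 23 and any common multi-resistance patterns added to Table 11 are not counted.

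**4. Chance of at least one p < 0.05 when the arms do not differ.** For k independent tests it is 1 − 0.95^k. For correlated tests it was simulated with two-sided normal statistics sharing a common correlation r. The values of r are assumed.

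| Tests counted | r = 0 | r = 0.3 | r = 0.5 | r = 0.7 | r = 0.9 |
|---|---|---|---|---|---|
| 2 (Table 10) | 0.098 | 0.094 | 0.09 | 0.08 | 0.07 |
| 10 (Tables 10-11) | 0.40 | 0.35 | 0.29 | 0.21 | 0.13 |
| 22 (Tables 9-11, post-enrolment) | 0.68 | 0.57 | 0.44 | 0.30 | 0.16 |

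The rows overlap by construction. In Table 9 the any-resistance row contains the two organism rows, and the both-organisms row lies within each of them. Table 10 largely aggregates Table 11. Where rows overlap heavily, the values at higher r are the more relevant ones.

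**5. The 0.05 level.** It is stated in words for the endpoint c tests with Table 9 cited. Tables 10 and 11 show only a chi-square p-value column, so 0.05 there is an inference.

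**6. Multiplicity statement.** The SAP gives a reason for making no adjustment at the interim analysis (4.1) and for using 0.05 in the exploratory subgroup analyses (4.2.5). It gives none for endpoint c.

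**The case against.** The strongest reply is that the plan already shows where the hypothesis is examined. The hypothesis concerns emergent resistance, the SAP defines one emergent indicator covering both organisms and all agents, and it sends that indicator to Table 10. Table 9 is called a summary, and Table 11 is introduced as a display of which antibiotics are involved. On this reading two tests are in play, not dozens, and longitudinal models would use both visits together. Endpoint c is also one of five secondary endpoints, and all of its rows are specified in advance.

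Most of this stands, and it limits the point. A reader might infer from the shells that the arms are compared in 28 equal tests at 0.05 (18 + 2 + 8). The documents do not support that: six of the cells are baseline comparisons, and the text gives Tables 9 and 11 partly descriptive roles. A reader might also quote one error rate, such as the 68% for 22 independent tests. That needs an independence that these overlapping rows cannot have. Nor do the documents show an intention to report whichever cell is significant.

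The reply does not remove the gap. Table 10 still has two p-values and no rule to combine them, and it is not the table cited for the 0.05 test. The longitudinal models are only to be explored, and they model status at each visit rather than the cumulative proportion.

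**Conclusion.** The point holds: endpoint c as defined is not computed by any planned output, no comparison is named as its test, and the multiplicity statement listed in Protocol 16.1 is missing for it. This follows from the text and shells alone and does not depend on the error-rate figures.

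The size of the multiplicity problem depends on what is counted. On the narrowest reading, the two Table 10 rows, it is modest: about 7-10% against a nominal 5%. It is about 13-40% over Tables 10-11 and about 16-68% over the 22 post-enrolment tests. Each range assumes a common correlation from 0.9 to 0, and the lower values are more relevant where rows overlap. The primary non-inferiority analysis is not affected. The SAP should be corrected before unblinding.

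**What to change.** 1. Define one indicator per child: emergent resistance, under the existing SAP 4.2.3 definition, at TOC or at Day 24-30.
2. Add it as a row in Table 10 with the difference between arms and a two-sided 95% CI, and name it as the single test of endpoint c at two-sided 0.05. That also supplies the multiplicity statement.
3. State how missing stool samples are handled. Population 4 (SAP 5.1) requires only a TOC sample, so the indicator is undefined for a child negative at TOC with no Day 24-30 sample. Give a main rule and a sensitivity analysis.
4. Label the by-visit, by-organism and by-agent results (the other rows of Tables 9-11) as descriptive or exploratory.
5. Reconcile the population for Table 9: the text of SAP 4.2.3 says Population 4, the shell says Population 2.

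The cost is one derived variable from data already collected, a missing-sample rule and SAP wording. The downside is that a result at a single visit or for a single agent can no longer be presented as confirmatory.
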